5.4 Primary Outcome Measure

Our primary outcome is HIV SSK return rate.

[figure not shown]
5.5 Secondary Outcome Measure

1. Point of delivery outcomes:
 - Acceptability of targeted HIV SSK distribution, including rationales for accepting or refusing the offer of an SSK
 - Acceptability and feasibility of targeted SSK distribution among specified service providers, including utility of protocols for SSK targeting, offers and intervention uptake.
2. Data collection outcomes:
 - Demonstration that intervention models and service provider training and support incorporates sufficient capacity to successfully record the numbers of: people offered SSK, accepting SSK, and returning SSK
 - Feasibility of collecting correct contact details enabling follow-up, reminders and communication of results
3. Pathway to care outcome measures:
 - Proportion of those whose samples are reactive who: a) are informed of results in person and b) who attend for confirmatory testing at an NHS setting of their choice
4. Overarching outcome measures:
 - Cost per person kit distributed and cost per HIV diagnosis per setting
 - Attrition rates and loss to follow up
 - Confirmatory testing, proportion of those receiving an HIV positive diagnoses, and clinical stage at diagnosis
 - Feasibility and sensitivity of outcome measures (testing, behavioural and economic) for a definitive trial.

6. Study Design

This is a prospective, mixed-methods, non-randomised study. The study evaluates the effectiveness of self-sampling for HIV as well as the cost effectiveness of distributing the SSK through GP settings and Community based organisations. Feasibility and acceptability will also be assessed through a process evaluation. Please see the fieldwork schematic diagram in section 6.1 for further information.

6.1 Fieldwork Schematic Diagram

6.2 Study Setting

The study will be conducted in GP Practices in London and Greater Glasgow. The NIHR Clinical Research Network in South London and the Scottish Primary Care Research Network in Glasgow, have been approached to assist with the recruitment of GP practices that can participate in the study. We will only approach GP practices which have relatively large numbers of Black Africans registered with them. The following clinic characteristics will be collected on all participating sites:

- The proportion of black Africans served by the practice.
- The known proportion of HIV positive patients and whether or not this information is collected.
- The number of practice nurses in each potential practice.
- Whether or not new patient checks occur and if these include HIV testing.
- Whether or not the practice has special interests e.g. travel or sexual health.

We will also recruit participants from community based organisations in London. We will only approach community based organisations with experience of targeting services for Black African people and delivering HIV prevention, and whose existing scale and scope of work with this population is strong.

6.3 Study Eligibility

6.3.1 Inclusion Criteria

To be recruited into the study, participants will need to be:

- Black African
- Without diagnosed HIV,
- 18 years of age or older
- Accessing GP practices or community based organisations that are taking part in the study.
- Able to provide informed consent.
- Able to read and understand English.

6.3.2 Exclusion Criteria

The following participants will be excluded from the study:

- Participants who do not provide a means of contact for result notification.
- Participants who are unable to provide informed consent.

6.4 Intervention Design

The HAUS study seeks to develop and test an intervention of targeted distribution of self-sampling kits (SSK) for HIV testing within health care and community services to determine if this will increase HIV testing in African communities. The kits will be distributed by Practice Nurses (PN) in GP clinics in both Glasgow and London, and in London also by Community Workers (CW) from community organisations as a part of their outreach. Those who distribute the kits will be supported by a programme of training on the delivery of the intervention and research governance. All procedures will also be outlined in an intervention manual (including data collection, result management and linkage to care- see appendix 6). Scripts will be provided to the distributors (see section 6.7) to facilitate study engagement. These resources will help the PNs/CWs to identify and approach black Africans, recruit participants to the study, explain the kit testing and study processes, collect baseline data and complete uptake and refusal logs. Participants will be given a plain language information sheet about the study and a description of how to take the sample (including a link to an online video of someone completing the test) and return the sample. UCLH will provide the clinical oversight for the study. They will subcontract The Doctors Laboratory (TDL) to process the samples. Samples will be sent to TDL via Royal Mail and negative results will be delivered directly to participants via text message (or phone call if only a landline number is provided). Management of all reactive results will be provided by Central and North West London (CNWL) NHS Trust as part of their existing clinical systems. Where a sample is reactive, the individual will be directly contacted by telephone by an experienced member of their clinical team to discuss the results, their implications and to make a clear referral for confirmation testing and care.

6.5 Self- sampling Kit

6.5.1 Description of Self-sampling Kit

The TINY collection device in conjunction with ROCHE Combi will be used for this study. The ROCHE Combi is a 4th generation assay, used for the detection of HIV p24 antigen and antibodies

to HIV-1 (Groups M and O) and HIV-2. This means it is suitable for detecting recently acquired HIV. It can detect HIV that was caught more than 4 weeks ago and is CE marked. The ROCHE Combi has a sensitivity of 100% (lower 95% CI 99.8%) and a specificity of 99.63% (95% lower CI 99.42). This test requires collection of a few drops of blood (obtained by pricking a finger with the supplied lancet) in a small collection tube. The test enables the specimen to be transported to a lab, by post, in a vial that contains preservatives, which stabilize the sample for up to 21 days if temperatures are between 4° C and 37° C.

Self-sampling negates the need for dedicated staff or special infrastructure for specimen collection. The kit can be used at a time and in a setting of the users' choice. Members of our study team have previously used the same or similar tests to screen MSM for HIV in England and Scotland. They have also developed instruction sheets, which provide a step-by-step guide to using the device.

6.5.2 Intended Use

The ROCHE Combi assay will be used to test for the presence of HIV antibodies in participants who consent to take part in the study. The package that will be handed to participants will include:

1. The TINY kit sample collection device (including self-retracting lancets)
2. A sample data form (see appendix 7) which requires three unique sample identifiers from the participants in order for the Laboratory to be able to process the sample and to enable result notification
3. Sample collection instruction sheet (please see appendix 8). This will provide the following details:
 - Information on how to collect the sample.
 - A link to a video demonstration of collecting the sample.
 - Information on labelling the sample and postage.
 - Information on what happens after the participant posts the sample to the laboratory.
 - Information on how the result will be communicated.
 - Information on various reasons why they may be contacted by clinical team
 - A reminder about completion of the acceptability questionnaire.
4. The acceptability questionnaire (see appendix 5).
5. Stamped addressed envelope for sample and questionnaire return to the lab.

6.5.3 Maintenance and Storage of Self Sampling Kits

UCLH-TDL will supply UCL with kits which have a unique identifier. This identifier will be unique to the city and the setting where it will be distributed, that is either GP or community setting in London or Glasgow. The kits will also have an expiry date which will be one month from the end of study recruitment.

The project manager will coordinate the delivery of kits to each study site, keeping records of distribution via the study database. Study sites will email the project manager when they anticipate that their kits will run out and these will be supplied to them by the project manager. The project manager will also record any requests for additional kits by study sites.

No special storage requirements are necessary for the kits however sites will need to keep all kits in a locked cupboard until distribution to avoid tampering and theft. As part of the study initiation of each site, the project manager will check that the kits are being stored correctly.

6.6 Screening Procedures

6.6.1 GP Practices

Practice nurses will go through their patient list each morning and identify patients scheduled to visit in each session who are potentially eligible to participate in the study. The eligibility criteria indicated in section 6.3.1 will inform the screening process. The details of potential participants will be entered onto the screening and enrolment log (appendix 3). Only patients on the screening log will be offered the opportunity to take part in the study. Data on patients who are known not to meet the eligibility criteria will not be collected. Reimbursement for the time taken to screen for potential participants will be met through CRN research support costs (NIHR CRN in London and the Scottish Primary Care Research Network in Glasgow).

6.6.2 Community Based Organisations

The eligibility criteria indicated in section 6.3.1 will be used to identify potential participants during routine outreach and the provision of other services by trained CBO workers. The details of these potential participants will be entered onto the screening and enrolment log (appendix 3). Reimbursement for the time taken to screen for potential participants will be met from the study budget.

6.7 Consent and Recruitment

6.7.1 Introduction

Any practice nurse or community worker delegated responsibility to participate in the informed consent process will be duly authorised, trained and competent to participate according to the ethically approved protocol and principles of Good Clinical Practice (GCP). During routine consultations or engagement with Black African people who fulfil the inclusion criteria, distributors will opportunistically provide information about self-sampling kits for HIV testing to eligible participants using the intervention script.

Distributors (PNs or CWs) will be required to use the appropriate script to guide them on how to initiate discussion about the study. The distributor will explain that their organisation is taking part in a research study looking at the acceptability and feasibility of using self-sampling kits for HIV testing among Black Africans. Interested eligible potential participants will be given the Participant Information Sheet (PIS) appendix 1 and asked to read it, and given the opportunity to ask any questions. If the eligible potential participant declines at this stage, the distributor will complete the information on the screening and enrolment log with as much information as the eligible potential participant is willing to provide. The distributor will enter this information from the screening log onto the study database using a link to the study database. The procedure for targeting and recruitment is detailed below.

6.7.2 Targeting and Recruiting

The distributor will aim to introduce and recruit eligible candidates to the research study. They will explain the benefits of participating and having an HIV. All distributors will answer questions and aim to alleviate any concerns participants may have. The script below initiates the recruitment process:

“We are currently involved in an important study that I wonder if you’d be interested in taking part in? We want to see if people will use HIV self-sampling kits. HIV treatments are so good now; that you can live a normal healthy life with HIV, and being on treatment also stops most people from passing on the infection. So we are trying to find new ways to offer testing as it’s the people who don’t know their HIV status who become unwell.

This study is looking at whether people from the Black African community would want to use these kits. It’s a great opportunity as most people don’t have access to them yet.

Testing is very easy. It's all in this kit, which you take home to use when it is convenient to you. Once you've collected the sample you put it in the envelope provided and pop it in the post.

A few days later you are contacted by a NHS health clinic via your mobile phone with the results. Most people testing will be negative. A few people will have a test suggesting they have HIV (this is called a 'reactive' test) and we would have to check the result is correct.

It's all completely private and confidential - no one, other than the clinic contacting you, will know your result unless you want them to. What do you think? Is this something that you may be willing to try?"

If answer = NO then go to section A

If answer = YES then go to section B

Section A

"That's absolutely fine. We would really like to understand why people do not want to participate in the study. On this card are some of the common reasons why people say no – "

(Hand participant card)

"Would you possibly be able to let me know if any of the numbers match with your own reason? And if so which numbers? Of course it is also ok if you do not want to give me a reason."

(Participant gives reason or declines to do so)

(If reason given then insert into participant screening and enrolment log)

(Contact ends)

Section B

"First we need to determine if you're eligible for the study. Are you aged 18 or older and do you consider yourself Black African?"

(NOTE: If asked, the term 'Black African' includes anyone who identifies themselves as Black African, whether they are migrants from Africa, African descendants or African nationals.

If answer = NO then go to Section B1

If answer = YES then go to Section B2

Section B1 Not eligible to participate

*“Thank you for taking the time to consider the study but you do not meet the eligibility criteria. If you would like to test for HIV then the easiest way would be to *.....”*

(NOTE: Answer varies according to options available e.g. standard blood test if in GP, referral to testing centre if in community)

Contact Ends

Section B2 – Eligible to participate

PN or CW hand participant the information sheet.

PN or CW copy SSK Unique ID to the consent form.

PN or CW hand participant the consent form and ask them to read it and consent to the statements to participate in the study.

PN or CW retrieve consent form from participant and check to make sure that all options marked as ‘essential’ have been consented to.

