6.7.4 Baseline data

Participants who are successfully recruited into the study should then be asked to self-complete a short baseline questionnaire. The baseline questionnaire (appendix 4) will collect kit specific identification number; name, contact details (mobile or landline number), demographics (age, gender, country of birth) and details about prior HIV testing and sexuality. The baseline questionnaire will be available in electronic and paper based formats. The mode used will depend on provider and user preference and whether internet access is available. If a paper based version is used, the data will need to be subsequently entered directly by the distributor onto the study database via a web link later that day. All study sites will be provided a study tablet by the research team.

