6.9 Sample Collection and Analysis

Participants will be required to self-collect a sample of blood using the TINY vial in the kit provided to them. As indicated in section 6.5.3, there will be instructions including a video link on how to collect the sample. Participants will also be required to complete the form with three unique identifiers (that is initials, date of birth and unique ID number) to enable the sample to be processed at the laboratory. The ID number will be pre-populated on both the lab form and the acceptability questionnaire.

UCLH will be responsible for the following:

1. UCLH via TDL will process samples as soon as they are received.

2. UCLH-TDL will send a CSV file for the study manager of returned samples to enable the manager to send out two reminder texts to participants whose kits have not been returned. This will be sent as an encrypted email.
3. UCLH-TDL will send a CSV file with results for each of the samples returned so that these results can be entered on the database by the study team. This will be sent as an encrypted email.
4. UCLH-TDL will collect the acceptability questionnaires returned with the sample, store them in a locked cabinet and pass these onto the study team.

[figure not shown]

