6.10 HIV Result Management

For each of the samples processed, the result can be reactive, non-reactive or no result/indeterminate. The results management will be shared between UCLH-TDL and CNWL:

1. In line with standard practice in most NHS sexual health clinics, negative results will be delivered by text message. UCLH-TDL will be responsible for the delivery of these messages. If a participant has only provided alternative contact means (landline or email) then UCLH will notify a named senior Health Advisor at CNWL who will assume responsibility for result notification as per clinic practice.
2. If consent to notify the GP has been provided (an option only applicable to those recruited via General practice) then the study manager will be responsible for informing the GP of negative results via secure email or registered address.
3. UCLH-TDL will let the senior study manager and CNWL know about any reactive results by secure encrypted email. Please note that at this stage, the names of participants with reactive samples are unknown to all parties as only initials are required with SSK return.
4. The Health Advisor at CNWL will use this information to retrieve personal information from the UCL Data Safe Haven (IDHS) to be able to link the sample to an individual. The Health Advisor at CNWL will retrieve the full name and contact details of the participant, and whether consent has been obtained to notify the GP.
5. The study manager will phone the Health Advisor to confirm access of test result and personal details.
6. The named CNWL Health Advisor will contact the participant by phone call and inform them of the reactive result and need for confirmatory testing. If consent is obtained from the participant they will arrange linkage into appropriate local services for confirmatory testing. Postcode data will be used by the Health advisor prior to contact to identify appropriate local services for any one participant. This will all be done without disclosure of participant details.

7. The Health Advisor will have follow up phone contact with all participants with a reactive result to ensure linkage to care has occurred. This will also provide an opportunity to identify any unexpected consequences of the testing process.

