8. The Health Advisor will be responsible for completing the Pathways into care outcome measures CRF (appendix 10), this will involve follow up phone calls to HIV services and the participant to ensure linkage to care has occurred. This information will be directly entered into the IDHS using the secure UCL portal. They will also be responsible for notifying the GP of the result where consent has been provided; this option will only apply to those recruited through General Practice.
9. If the result is indeterminate, UCLH-TDL will highlight this result in the CSV file of results sent to the study Manager. The study manager will retrieve personal details from the IDHS database and pass these onto the clinic. One of the Health Advisors from the clinic will inform the participants of the indeterminate result and request permission for the study team to send them another kit or for them to attend an alternative testing venue. The Health Advisor will be responsible for completing the Pathways to care outcome measures CRF (appendix 10) again using the secure UCL portal to the IDHS.

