5.2 Personal Details

Do you not already have my personal information? (PN only)

"Yes we do have personal information on you in the surgery but as this is for a specific research study, we need to ask you for information for the purposes of the study"

Why do I need to give my personal information?

“We require you to give personal information so that your sample can be identified at the lab and you can be contacted with your test result. “

Who will have access to my personal information?

“All kits are returned to the University College London Hospital NHS Foundation Trust, who will keep a confidential record of your test result. Central & North West London NHS Trust will manage all those with reactive results or samples that are unable to be processed so they will also keep a record of those results. They are a sexual health service and will not divulge any details to anyone else unless you provide explicit consent for this to occur. Any identifying information needed for research purposes will be held on a very secure database at UCL with access limited to a senior member of the research team. All identifying information will be destroyed as soon as possible. Otherwise all the information will be anonymised for research purposes. Even the laboratory processing your sample will not know your name, only your initials, date of birth and phone number.”

How will my contact details be used?

“Your contact details will be used by NHS staff to contact you with your test result. In the case of a reactive or indeterminate test result, the NHS sexual health service involved with this study will contact you to discuss your options and ensure all the appropriate next steps to determine if the test result is correct are undertaken.”

How will my contact details be stored?

“Your information will be stored on encrypted hard drives at University College London. These are located within extremely secure networks and no one outside the research or NHS team can use them. I will not have access to any of the details you put into the system today, or any of the information you give to the study team later on.”

I don't have a mobile number I can use

“What we can do is we can take a landline number and the sexual health team involved with this study can call you to give you your test results.”

Will you do any other testing on the sample such as DNA?

“No we will not carry out any form of testing on the sample you submit other than the HIV test”

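### The recruitment script and one manual reply describe access to results and personal details more narrowly than the protocol's own data flow allows

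*Protocol*

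**What the plan says.** **Who will know the result.** Section 6.7.1 requires distributors to use a script. The script in 6.7.2 closes with the assurance that "no one, other than the clinic contacting you, will know your result unless you want them to". It is spoken before the information sheet and consent form are handed over (Section B2 of the script).

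**Where results go.** Under 6.9, the laboratory sends the study "results for each of the samples returned so that these results can be entered on the database by the study team". Under 6.10 item 3, "UCLH-TDL will let the senior study manager and CNWL know about any reactive results by secure encrypted email". Under item 9, for indeterminate samples, "The study manager will retrieve personal details from the IDHS database and pass these onto the clinic". Section 6.8.1 has the research team link both questionnaires to the test result through the kit number.

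**What the consent items cover.** The list in 6.7.3 includes contact by the NHS provider to give the result and, as an option in general practice, notification of the GP. No item mentions the study team seeing the result.

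**Who will see the personal details.** In the intervention manual (Appendix 6), section 5.2, the distributor's reply to a question about storage of contact details includes "I will not have access to any of the details you put into the system today". For the paper baseline questionnaire, however, protocol 6.7.4 says "the data will need to be subsequently entered directly by the distributor onto the study database" later that day. Manual 4.3 repeats this and also has the distributor take the form back and check that it is complete.

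**The concern.** The script describes a narrower circle of people than the protocol sets up. A participant who takes it at face value would not expect anyone on the research team to hold the HIV result. One who has asked about storage and then completes a paper form has been told something that the next step contradicts.

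This matters more here than in most studies. Phase 1 (4.2.1) lists privacy among the reasons self-sampling was acceptable, and the script uses confidentiality as its final inducement. Acceptability is part of the primary objective (5.2), so acceptance should be measured under a true description of who sees what.

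**Working it through.** The check is mainly a comparison of statements, with simple arithmetic for the size.

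**1. Script against result flow**
- Script (6.7.2): only the clinic making contact knows the result, unless the participant wishes otherwise.
- 6.9 item 3: results for all returned samples go to the study team. The study team is not the clinic making contact.
- 6.10 items 3 and 5: the study manager is told of each reactive result, and phones the Health Advisor to confirm that the result and personal details have been accessed.
- 6.10 item 9: the study manager can retrieve personal details from the safe haven. An indeterminate result reveals no HIV status, because manual 1.3 defines it as the laboratory being unable to get a result. What the item shows is that the person who receives results also has a route to identities.
- 6.8.1: the research team links results to questionnaires.
- The script's exception for the participant's wishes does not cover this, because no item in 6.7.3 asks about it.

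The script sentence and the data flow cannot both be true.

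**2. Manual reply against paper entry**
- Manual 5.2: the distributor will have no access to details entered that day. The reply is not limited to tablet use.
- 6.7.4 and manual 4.3: the distributor retrieves, checks and keys the paper form.
- Appendix 4: the form carries name, date of birth, phone number, last HIV test and sex of partners.

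The reply can be true for tablet entry. It is untrue for paper.

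**3. Size**
- Planned participants (section 3): 1580. Assumed return (7.1): 50%. Results reaching the study team: 1580 × 0.50 = 790.
- Expected reactive results among these use prevalence p of nearly 4 in 100 (manual 1.1) or 1 in 20 (manual 5.1), one third undiagnosed (manual 5.1), sensitivity 100% and specificity 99.63% (6.5.1). The undiagnosed share among people without a diagnosis is (p/3)/(1 − 2p/3).
  - p = 0.04: 0.01333/0.97333 = 0.01370; 790 × 0.01370 = 10.8 true reactive; 0.0037 × (790 − 10.8) = 2.9 false reactive; total 13.7.
  - p = 0.05: 0.01667/0.96667 = 0.01724; 790 × 0.01724 = 13.6; 0.0037 × (790 − 13.6) = 2.9; total 16.5.
- Paper forms: the protocol gives no share, so anywhere from 0 to 1580. The number who both ask the storage question and use paper is smaller and unknown.

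**The case against.** The strongest reply is that the script only opens the conversation. An information sheet and a consent form follow, and section 8.1 says participants will be told that the research team uses their study data. Neither form is at hand, and either may describe research access fully. This stands as a limit on the conclusion. It does not make the script sentence true: a correct information sheet would contradict what the distributor had just said.

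Second, results do not travel under names. Samples are identified by kit number, initials and date of birth (6.9). Section 6.10 item 3 notes that names are unknown to all parties when a reactive result is reported, and item 4 has the clinic's Health Advisor, not the study manager, retrieve the name. This also stands, and the 790 results should not be read as named disclosures. The assurance still fails, because the study manager can re-identify participants and the script makes no distinction between named and coded results.

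Third, the study manager's reporting of negative results to GPs happens only with consent, which the script's own exception largely covers. That example is not relied on here.

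Fourth, the distributor's denial is heard only by participants who ask. The manual lists paper copies for when online services are unavailable (3.1, 3.2), and someone handing a form back can see who receives it. This narrows the second contradiction but does not remove it: 6.7.4 and manual 4.3 also let preference decide the mode. The fuller manual answer about who has access is likewise given only on request.

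A reader might go further and infer that consent is invalid, or that the promise raises uptake and distributor access biases answers on partners and testing, so that the data would not carry over to phase III. The protocol supports neither inference. The consent documents are unseen, and nothing gives a size or direction for any such effect. Phase 1 finding 12 (4.2.1) even suggests that participants accept a trusted professional collecting personal details for a study.

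**Conclusion.** Two scripted oral assurances are inaccurate against the protocol's own procedures. The result promise in 6.7.2 is wrong for every returned sample: about 790 at the assumed 50% return, of which about 14 to 16 would be reactive if those returning kits have the manual's population prevalence and every kit yields a result. The manual 5.2 reply is wrong whenever it is given to someone who uses the paper form, a number the protocol does not let one estimate.

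The finding is confined to the wording of these assurances. Invalid consent is not shown, and an effect on uptake or baseline answers is possible but unquantified. The wording should be corrected, because the change is specific and cheap, and it lets acceptability be assessed under a true description.

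**What to change.** - Reword the script sentence in 6.7.2, and anywhere the manual repeats it, to match 6.9 and 6.10. For example: the NHS laboratory and clinic and a small number of authorised study staff will see the result, and no one else without the participant's consent.
- Limit the reply in manual 5.2 to tablet entry, and add that the distributor enters paper forms.
- Check that the information sheet and consent form say the same, including that the study team receives results.

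The cost is a few lines of text and a less absolute privacy promise, which might lower acceptance slightly. Data flow and result notification do not change.

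Splitting Appendix 4 into a contact page and a sealed questionnaire page is an option, not part of this recommendation. It would keep sensitive answers from the distributor, but it removes the distributor's completeness check and could increase missing baseline data.
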